## **4. Risk/benefit assessment**

### 4.1. Importance of the knowledge to be gained

Substance use accounts for more morbidity, mortality, and disability than any other preventable condition, yet only a small fraction of individuals with unhealthy substance use are served by the specialty treatment system. The technology-assisted approach to screening and intervention that we

propose to study aims to reduce barriers to addressing substance use in primary care patients. This innovative model for a primary care-integrated approach to unhealthy substance use has the potential to improve population health related to drug and alcohol use.

#### **4.2.Risks**

This study poses no more than minimal risk to participants. The main risk of participation is loss of confidentiality, which will be guarded against by the measures detailed below. As an additional protection, we will apply for a NIH/NIDA for a Certificate of Confidentiality. Personal identifying information collected for the study will be kept to the minimum required to collect the specified study measures.

*Primary care providers:* Providers are employees of the study sites Adequate protections will be implemented to ensure that participation in the research does not jeopardize their employment or professional standing. No information about personal substance use will be solicited. Rather, the information gathered will address practice patterns and professional opinions. Provider participants at enrollment only sites will have the same protections as those at the main study sites (Bellevue and Gouverneur Health).

*Patients:* There is a possibility that participants may feel uncomfortable while completing some study assessments. We will minimize discomfort by having interviews conducted by a trained and qualified research assistant, and in a private space. Participants will be informed that all aspects of their participation are voluntary and that they may choose not to complete assessments or to discontinue their participation entirely, without repercuSSION or penalty.

In Phase 2, samples are collected from patient participants for hair testing at the 6-month study visit. This will detect common drugs of abuse, as a means of corroborating self-report of recent drug use. Results of hair testing will not be shared with the patient or medical provider. If a participant has to result in having their 6 month interview over the telephone, they will not be required to give a hair sample. This will not have a substantial impact on our findings, as the hair analysis results are only one of many secondary measures (for Aim 3). The primary Aim 3 measure is self-reported drug use, assessed by timeline follow-back interview, which will be done by phone. There are thus two exclusion criteria for the hair sample: (1)having no hair on the head that is at least one-and-one-half inches long; and if the interview is conducted over the phone. RAs will be trained in hair collection procedures through an on-line training provided by the testing company (Omega Laboratories, Inc.). Hair samples will be collected by the RA following the Omega Laboratories collection protocol. Hair samples will be obtained by snipping one-and-one-half inches of head hair using scissors, cut close to the scalp, preferably snipped from the vertex posterior, located at the back of the head, just below the crown. Approximately 60-80 strands of hair are required (in general, the amount needed is the thickness of a shoelace tip). If necessary, hair can be collected from several locations on the head and combined to obtain the required amount of hair. If head hair is not available, body hair may be collected from the axilla(e) or chest. The sample will be identified only by the participant's Study ID, which will be recorded on the Omega Laboratories collection envelope. Samples will be mailed to the Omega laboratory for analysis on the same day they are collected.

#### **4.3.Protections against risks**

**4.3.a. Informed Consent:** Informed consent will be obtained by the researchers from all participants, as per the human subjects research procedures described in Section 5.2. It will be made clear to patients that participation is entirely voluntary. Study staff will err on the side of caution (i.e. lack of eligibility) in deciding if someone is cognitively able to give consent and participate in the study.

**4.3.b. Treatment Referral:** Individuals who are identified as having high-risk use of alcohol or any

drug during screening, or who self-report pregnancy at baseline, will not be enrolled in the study. They will be linked to the primary care clinic's Social Worker, or that designated clinics' behavioral health care staff, for referral to appropriate substance abuse treatment. Referrals may be made to on-site resources or off-site treatment facilities. The social worker, with assistance from the research team, will facilitate entry to treatment. Bellevue Hospital's addiction treatment services, also serve patients from Gouverneur Health, and are anticipated to be the primary referral site for both of the main study sites. Bellevue offers a wide range of treatment services, including a structured outpatient drug and alcohol treatment program, dual- diagnosis treatment for individuals with co-occurring psychiatric and addiction disorders, and opioid addiction treatment medication (provided through an office-based buprenorphine treatment and a methadone maintenance treatment program). Participants from enrollment only sites, or those from main study sites who prefer to seek treatment outside of Bellevue Hospital, or whose needs may be better met elsewhere, will be offered referral to outside programs by the social worker, or other behavioral health care staff. These patients will additionally receive from the research staff a printed resource list of treatment options, including information on intake procedures. Tobacco screening and cessation assistance are already integrated into usual care at the participating primary care clinics. Bellevue Hospital also has a smoking cessation program, offering group and individual counseling and access to pharmacotherapy, which is available to all clinic patients at the main study sites.

Because all patients being screened for study eligibility are current patients of the primary care clinics or Virology clinic where this study is being conducted, they have the opportunity to seek assistance from their primary care provider or other resources (for example, social worker, nurse, mental health provider, etc.) in the clinic. Participants with PHQ or GAD scores indicating severe depression or anxiety will be advised to speak to their primary care provider and referred by the RA to the psychiatry psychiatry walk-in clinic, or emergency room. Patients who become pregnant during the study will not be withdrawn, but they will be advised by research staff to discuss pregnancy and substance use with their PCP and other clinical staff (OB/GYN, nurse, social worker, etc.). The participating clinics are well equipped to provide patients the behavioral health and other supportive care they need. These resources are provided as part of regular care in the study clinics, and patients will not be restricted from accessing them in any way. Medical and psychiatric emergencies will be handled according to the study's Standard Operating Procedures (SOP).

**4.3.c. Privacy and Confidentiality:** The personal identifying information collected for the study is kept to a minimum. All consent processes and study assessments will take place in private rooms. Focus groups and interviews will be held in a private room, and will include only participants and members of the research staff. Participants will be informed that audio recordings are made of the focus groups, interviews, and medical visits. For medical visits that are being recorded, the RA will place a digital audio recorder in the exam room and begin recording when the patient and PCP both enter the room. The RA will stop the recording and take possession of the digital recorder as soon as the patient exits the room. The patient and PCP will have the option of stopping or pausing the recording at any time.

Several measures will be taken to insure the confidentiality of the data. Confidentiality will be maintained at all times through the use of unique study numbers on all assessments. We will apply for a Certificate of Confidentiality from NIH/NIDA. Information concerning the Certificate of Confidentiality and its implications will be provided to participants in the consent form(s).

For patients who enroll in Phase 2, the researchers will collect contact information (telephone numbers, address, and email address) to facilitate study retention and scheduling of follow-up study visits. Because in this urban safety net primary care population patients may have unstable housing, participants will also be asked to provide contact information for at least three close

contacts (family, friends) who the researchers could contact by phone or mail if they were unable to locate the participant using their personal information. No personal information will be shared with these close contacts. We will also ask if they work with a social worker or case manager, and if they would allow us to contact them if we were unable to locate participant using their personal information.

For participants in the SUSIT study phase, the research staff will send a clinical reminder to the patient's PCP at each scheduled medical visit that occurs during the study period. Research staff will send these reminders using email or the clinic's secure EHR-integrated message system. It will be sent directly to the PCP only, and will not be accessible to any other than the PCP and the research staff who sent the message. The message sent to the PCP will include the patient's name, medical record number, and substance use screening results from the baseline visit.

At enrollment only sites, the NYU research staff will not access the EHR to view patient information or to communicate with the patient's PCP. The research staff will communicate with PCPs through either secure H+H System email or secure NYU email communications only, and will work with participants and front desk staff to determine the patients' upcoming scheduled appointments.

Transcripts will not contain names or other information that could be used to identify individuals. Participants will be informed in the informed consent sheet that these sessions are recorded for purposes of transcription. Data will be analyzed and reported anonymously.

All study personnel have already taken or will take the mandatory training required by their IRBs, including HIPAA and Patient Privacy/Confidentiality training, to ensure that they are aware of the importance of patient confidentiality and all appropriate laws regarding the protection against patient privacy breaches. Procedures will be in place to ensure that all files containing patient information will be kept in locked filing cabinets and/or password-protected electronic databases. There will also be a system in place for breaches in patient privacy or other adverse events to be reported to the study PI, who will take the appropriate steps to ensure that they are documented and that there is minimal risk that it could happen again.

#### **4.4. Potential benefits to the subjects**

There are no direct benefits to patients or primary care providers participating in the study. Participants will receive incentive payments that compensate them for the time spent in study activities. The community at large, including patients and providers, benefits from knowledge gained about substance use, screening and assessment methods, and medical practice that is gathered through this study. The risks to subjects mentioned above are reasonable in relation to these anticipated benefits.

### **5. Subject identification, recruitment and consent**

#### **5.1. Method of subject identification and recruitment**

The study protocol and informed consent documents will be reviewed and approved by the Institutional Review Boards of NYU and New York City Health and Hospitals before enrollment begins. Consent will be obtained by trained research staff. Participants will be given a written consent form that includes required language regarding HIPAA and the Certificate of Confidentiality, as well as name and contact information of the PI and of the institutional review board, a description of the study, the payment schedule, a description of potential risks and benefits, a statement of confidentiality, and an indication of the right to refuse or withdraw participation at any time without any consequence. Research staff will review this form verbally and in detail with participants.

*Primary care providers:* PCPs will be recruited by the researchers via faculty meetings, email, and in-

***Patients:*** Patient participants will be recruited from the adult primary care and virology clinics of Bellevue Hospital or the adult primary care clinic at Gouverneur Health, and from the enrollment only sites. The research team will obtain from the clinic administrator, on a weekly basis, a list of patients scheduled to see participating PCPs for a routine medical appointment. Patients will be approached by a RA in the waiting room, when they present for their medical visit. The RA will inform them of the study, and obtain verbal consent to screen them for study eligibility. Research staff will not have any information about patients of non-participating PCPs, and no patients of non-participating PCPs will be approached by the RA.

**Screening for study eligibility:** Patients who agree to screening for eligibility and meet the inclusion criteria for age and language will receive the tablet-based screening tool. The screening tool will be described as a 'computerized questionnaire about health behavior', to avoid biasing participant responses. The RA will present interested patients with an information sheet, and will be present and available for patients who have any questions. Patients will be required to provide verbal consent to proceed. Those who agree to participate will be assigned an anonymous study ID by the screening tool. Those who agree to continue the screening process will self-administer the substance use screening questionnaires on the tablet computer. When substance use screening is complete, research staff will view the patient's substance specific involvement scores (SSIS) on the tablet computer. Patients having moderate-risk use of at least one drug (SSIS 4-26 for any drug), in the absence of any high-risk drug or alcohol use (SSIS 27+ for any drug or alcohol), and meet all other inclusion/exclusion criteria, will be offered participation in the main study. Individuals who do not qualify for the study due to high-risk drug or alcohol use will be informed by research staff of their risk score and its interpretation. They will be offered treatment referrals as detailed in section 4.3.

## **5.2. Process of consent**

***Primary Care Providers:*** For interviews and usability testing activities, a member of the research team will obtain consent in English and/or Spanish via an IRB-approved consent form (described in Section 5.4 below). Participants will provide consent for audio recording of focus groups, interviews, and medical visits. PCPs participating in Phase 1 usability testing will provide consent for both audio and video screen recording, and those participating in Phase 2 will provide consent for audio recording.

Signed consent forms will be filed in a secured cabinet located in the offices of the research team at NYU School of Medicine.

***Patients:*** Patients recruited to Phase 1 will receive paper copies of an information sheet, and will be asked to provide verbal consent for participation. Patients recruited to Phase 2 (SO and SUSIT conditions) will be asked to sign a written consent document. For participants at Bellevue only there will be one copy of the enrolled patient consent form made for the Clinical Research Center at Bellevue, where interviews are conducted. Those consent forms are stored in a double locked unit at the Clinical Research Center (CRC) in Bellevue and only the CRC staff has access to the record room. At all other study sites, including enrollment only sites, interviews will be conducted in a private room that is not located in the CRC, and no copy of the consent form will be made.

Individuals who enroll in a study phase that requires having their screening results delivered to the PCP (i.e. Phase 1 clinical testing phase, or Phase 2 SUSIT condition) will additionally sign a HIPAA authorization for sharing their screening results with the medical provider. Patients who choose to enroll in Phase 2 SUSIT condition will go through a detailed information sheet which will review procedures for sharing the screening results with their provider, the RAs will obtain verbal consent to share those results with their PCP. A separate signed authorization for Audio Recording will be collected before patients meet with their provider.

Beginning in January 2019, for Phase 2 patient participants we will obtain consent to allow the research staff to review primary care provider notes that are documented in the patient's medical during the 12 months following study enrollment (inclusive of the date of enrollment). For participants enrolled in the SUSIT phase, the chart review is included in a revised IRB-approved informed consent document (version date 01/09/19). Participants who previously completed informed consent will be re-consented using the revised informed consent document when they come back for any follow-up appointment with their primary care provider, or at their 3 month or 6 month follow-up study visits.

Participants who were previously enrolled (in the SO or SUSIT phase) and have completed all study visits, and who are not able to meet with research staff in person to complete the revised informed consent document, we will obtain verbal consent over the telephone. In the telephone consent process, research staff will provide information verbally about the study using an IRB-approved script, and will offer to send participants a written information sheet (via regular mail and/or email, depending on the participant's preference). Participants will be given an opportunity to ask questions, and then will be asked to give verbal consent for the chart review. If we cannot reach a study participant over the telephone or in person, we will not conduct the chart review for that individual.

For PCPs and patients, the RA will meet individually with the potential participant, after they have finished with their PCP, in a private area of the clinic and give them a copy of the consent document. The RA will review the contents of the consent document, which contains a description of the purpose of the study and the participant's rights of confidentiality, and review the remaining study activities (which are the baseline and follow-up research assessments). The RA will offer to answer any questions. Following this discussion, and prior to any collection of any study-related information, consent to participate in the study will be obtained. The written consent may be obtained either before or after the visit with the primary care provider, depending on the amount of time that is available (i.e. if patients are called to see their provider before the full consent process has been completed, or if the patient is more comfortable doing this after the visit, the signed consent may be obtained after the patient finishes their visit with the provider).

The 12 patient participants who are recruited to take part in an individual in-depth interview will be purposively recruited from the already-enrolled sample of study participants to achieve a distribution of gender, race, and age. These individuals will receive a written information sheet prior to the interview, and will be asked to provide verbal informed consent for the interview and for audio recording.

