In both the SO and SUSIT conditions, study visits are at baseline (same day as the primary care visit), 3 months, and 6 months. Exit surveys ascertain what elements of brief intervention were conducted by the PCP, and are conducted at the baseline visit, the 3 month, the 6 month and at each follow-up medical visit. If the patient has not seen their provider in the last 3 months, they will not have to complete the survey. To minimize any potential for the RA to influence reporting, patients will self-administer the exit survey, prior to collection of additional substance use measures. PCPs will receive a clinical reminder for patients in the SUSIT condition, and may consequently address substance use differently than in the SO condition. For this reason, we will record scheduled follow-up medical appointments, and call, email or text participants several days prior to appointments.

At the baseline study visit, and at the 3- and 6-month study visits, the RA will administer substance use assessments: Timeline follow-back (TLFB), Composite International Diagnostic Interview, Second Edition, Substance Abuse Module (CIDI-SAM), for Spanish speaking patients the M.I.N.I (Mini-International Neuropsychiatric Interview) will be used as the measure of substance use disorder, because the CIDI is not currently available in Spanish, the Short Inventory of Problems for alcohol and drugs (SIP and SIP-DU), the first 8 items of the Patient Health Questionnaire (PHQ-8), and the Generalized Anxiety Disorder 7-item scale (GAD-7). Participants will provide hair samples for drug toxicology testing at the month-6 study visit. This will detect common drugs of abuse, as a means of corroborating self-report of recent drug use. If after repeated outreach attempts, and the participant is still not able to meet with RA in person, a phone interview will be scheduled with the participant for either the 3 or 6 month follow-up interview. This will be a one-to-one phone interview, with the RA or RC (whomever is conducting the interview) will be a private area. When scheduling the phone interview will ask the participant to ensure being in private space during the phone interview. For those participants that will have their 6 month interview by phone, the hair sample will become not applicable for those participants.

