Chart review: Research staff will perform a structured chart review of the participant's medical record that examines the content of notes written by the participant's primary care provider(s) during the 12 months following study enrollment (inclusive of the date of enrollment). The chart review collects similar information to the patient exit survey; namely, documentation of any discussion by the primary care provider about drug, tobacco, or alcohol use. The chart abstraction form will be approved by the IRB.

Individual in-depth interviews with patient participants will characterize the acceptability to patients of conducting substance use screening and interventions in primary care. A purposive sampling approach will be used to select 12 patients who are already enrolled in the SO or SUSIT arm of the study. Those selected will represent a range of sex and age groups. The attitudes of patients are particularly important when addressing a stigmatized behavior such as substance use. While self-administered screening tools may allow for more honest reporting of stigmatizing behaviors, some patients might prefer face-to-face communication with their providers.

Table 1. Phase 2 Outcomes and measures

Outcome	Measures	Source	Collected at
Primary Outcome:			

Patient receipt of a substance use intervention	Audio recordings of medical visits, transcribed and coded with BAS scale	Audio recording of medical visit	Baseline and all follow-up PCP visits (SUSIT condition only)
	Patient exit survey: -Frequency of intervention -Elements of intervention	Patient (self-administered)	Baseline and all follow-up PCP visits
	Chart review -Frequency of intervention -Elements of intervention	Medical Record	Baseline and all follow-up PCP visits
Secondary Outcomes:			
Disclosure of substance use on screening	ACASIASSIST vs. TLFB and hair test results	Patient	Baseline 3- and 6-month study visit*
Self-reported drug and alcohol use	90-day TLFB	Patient	Baseline 3- and 6-month study visits
Drug or alcohol use severity	CIDI-SAM	Patient	Baseline 3- and 6-month study visits
Problems related to drug or alcohol use	SIP, SIP-D	Patient	Baseline 3- and 6-month study visits
Psychological well-being	GAD-7, PHQ-8	Patient	Baseline 3- and 6-month study visits
Biologic measure of any drug use	Hair testing	Lab result	6-month study visit*
Acceptability to patients of screening and interventions	In-depth interviews	Patient	Individual interviews with 6 patients in each study period

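### Telephone consent for chart review is written only for earlier enrollees who completed every study visit, so a primary-outcome source can go missing according to follow-up status

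*Combined protocol and SAP*

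**What the plan says.** Section 5.2 gives three routes to consent for chart review in Phase 2.

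- **At enrollment.** For the SUSIT phase, "the chart review is included in a revised IRB-approved informed consent document (version date 01/09/19").
- **In person, for those who had already consented.** They are re-consented "when they come back for any follow-up appointment with their primary care provider, or at their 3 month or 6 month follow-up study visits".
- **By telephone.** This route is for those already enrolled "in the SO or SUSIT phase) and have completed all study visits, and who are not able to meet with research staff in person".

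The passage then closes with: "If we cannot reach a study participant over the telephone or in person, we will not conduct the chart review for that individual". That sentence has no completer condition.

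Table 1 lists three measures of the primary outcome: audio recordings (SUSIT only), the patient exit survey, and chart review. Section 3.1.b says of the last: "The chart review collects similar information to the patient exit survey". The review covers primary care notes "during the 12 months following study enrollment (inclusive of the date of enrollment"). Exit surveys "are conducted at the baseline visit, the 3 month, the 6 month and at each follow-up medical visit".

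**The concern.** The conditions on the telephone route are joined by *and*. An earlier enrollee who missed month 3 or month 6 fails one of them, however easy that person is to reach by phone. The only other written route for earlier enrollees needs a return in person after January 2019, when this consent process begins. No reason is given for limiting the calls to completers.

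Once consent is given, chart review needs no attendance and no questionnaire. It is therefore the measure best placed to fill gaps left by people who stop taking part. Followed as written, the rule removes some of those people from it and keeps those with more contact, who had more chances of an intervention. The analysis in section 3.2.a, whether any intervention occurred in at least one visit, states no method for missing data.

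**Working it through.** **Step 1. Who has a written route.** Setting the sentences of section 5.2 side by side:

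| Enrolled | Study visits | In-person contact after January 2019 | Written route |
|---|---|---|---|
| SUSIT, on the revised form | any | not needed | at enrollment |
| Earlier (SO or SUSIT) | all completed | yes | in person |
| Earlier | all completed | no | telephone |
| Earlier | one or both missed | PCP visit or a remaining study visit | in person |
| Earlier | one or both missed | none | **none** |

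The gap is the last row. The closing sentence says when review will not occur. It implies that anyone might be phoned, but it does not provide for calls to non-completers. The two sentences point different ways.

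**Step 2. What is lost in that row.** The chart window opens on the day of enrollment, but re-consent could only start in January 2019. A person in the last row may already have charted visits: the baseline visit always, and any later PCP visit before contact ended. The baseline visit has a planned exit survey as well. A later PCP visit at which no exit survey was completed would be documented only in the chart (or, in SUSIT, on a recording).

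**Step 3. Whether conditions can differ.** The revised form is described for the SUSIT phase only, so SO participants appear to fall wholly among earlier enrollees. SUSIT participants are split between earlier enrollees and those on the revised form, in proportions that the protocol does not give.

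**Step 4. Size.** There is no figure in the plan to reproduce: it gives 75 patients per condition and no retention rate. The following is illustration.

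Inputs: n = 75 per condition (section 1.3); non-completion r = 10% to 30% (assumption); receipt of intervention 40% in completers and 20% in non-completers (assumption).

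- Number affected = 75 × r. At 10%: 7.5, about 8. At 20%: 15. At 30%: 22.5, about 23.
- True receipt = (1 − r) × 0.40 + r × 0.20.
- Overstatement if only completers have charts = 0.40 − true receipt = 0.20 × r.

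| r | True receipt | Completers only | Overstatement |
|---|---|---|---|
| 10% | 0.38 | 0.40 | 2 points |
| 20% | 0.36 | 0.40 | 4 points |
| 30% | 0.34 | 0.40 | 6 points |

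Under these assumptions the figures are upper bounds. They treat all 75 as earlier enrollees, which is too many for SUSIT if anyone there signed the revised form. They also treat every non-completer as lost, although some will return and be re-consented.

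**The case against.** A reader might infer three stronger claims, which the documents do not support.

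- *Dropouts get no chart review unless they return to their PCP.* Not so in general. SUSIT patients on the revised form consent at enrollment, and later dropout does not undo that. Earlier enrollees can also be re-consented at a remaining 3- or 6-month study visit.
- *The chart is the only follow-up source of the primary outcome for dropouts.* Not so. Exit surveys, and recordings in SUSIT, are planned at follow-up PCP visits, which are not study visits. Someone who skips month 6 but sees the PCP can give an exit survey and re-consent that day. Someone who never sees the PCP after baseline has no later PCP visit to chart.
- *The SUSIT versus SO comparison is biased in a known direction.* Not shown. The number of SUSIT patients on each form is not given. Section 4.3.c also bars staff from the EHR at the enrollment only sites, which take part in SUSIT alone, so consent there need not yield a chart.

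Two further objections have some force. Section 3.1.b allows phone interviews at month 3 or 6. If these count as visits, a reachable person still in follow-up can become a completer. This does not help those whose interviews were missed altogether. Also, the completer condition may have been meant as shorthand for participation being over, which would fit the closing sentence. That is a fair reading of intent, but staff applying the sentence as written would not phone a non-completer.

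What stands is the last row of the table: a narrow group, selected on follow-up, with no clear written route.

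**Conclusion.** The point holds in a limited form. For participants enrolled before the revised form, section 5.2 does not clearly provide telephone consent unless every study visit was completed, and its closing sentence conflicts with that limit. Taken literally, chart review is lost for those who missed a study visit and have no later in-person contact, and the loss depends on follow-up status. It may be unequal between SO and later SUSIT enrollees.

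Its size cannot be established from the documents. The ceilings of 8 to 23 of 75 patients and 2 to 6 percentage points rest on assumed non-completion and receipt rates, and the true effect would be smaller wherever non-completers return. Exit surveys limit the damage to the primary outcome as a whole. The case for acting is that the missingness is avoidable and nearly free to reduce.

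**What to change.** In section 5.2, delete the condition that all study visits be completed. Suggested wording: *For any previously enrolled Phase 2 participant who has not withdrawn and was not re-consented in person, verbal consent for chart review will be sought by telephone, whether or not the 3- and 6-month visits took place.* The exception for withdrawal keeps faith with the right to leave without consequence in sections 4.2 and 5.1. Align the closing sentence so that both name the same group. In the analysis, report chart availability by completion status and condition.

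The cost is a minor IRB amendment and a few more calls. The telephone script (section 5.2), the chart review information sheet (section 5.4) and participants' contact details (section 4.3.c) are already provided for.
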